7.8.8.1.2. Hospitalizations for Adverse Event

Hospitalizations for AE will be summarized, including number of events, total number of days hospitalized, the rate of events and days hospitalized per person-year.

Hospitalizations will be provided in a by-subject listing.

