6.1.2. Secondary Objectives

The key secondary objectives of the study are:

- To compare the complete remission (CR) rate between AG-120 + azacitidine and placebo + azacitidine.
- To compare OS between AG-120 + azacitidine and placebo + azacitidine.
- To compare the CR + CRh rate between AG-120 + azacitidine and placebo + azacitidine; CRh will be derived by the Sponsor.
- To compare the ORR between AG-120 + azacitidine and placebo + azacitidine.

Additional secondary objectives are:

- To compare the CR + CR with incomplete hematologic recovery (CRi) (including CR with incomplete platelet recovery [CRp]) rate between AG-120 + azacitidine and placebo + azacitidine.
- To compare duration of CR (DOCR), duration of CR + CRh (DOCRh), duration of response (DOR), and duration of CR + CRi (including CRp) (DOCRi) between AG-120 + azacitidine and placebo + azacitidine.
- To compare time to CR (TTCR), time to CR + CRh (TTCRh), time to first response (TTR), and time to CR + CRi (including CRp) (TTCRi) between AG-120 + azacitidine and placebo + azacitidine.
- To assess the safety and tolerability of treatment with AG-120 + azacitidine compared with placebo + azacitidine.
- To compare transfusion requirements (platelet and red blood cell [RBC]; number of units transfused), infection rates, days spent hospitalized, and other efficacy and safety measures that are potentially indicative of clinical benefit between AG-120 + azacitidine and placebo + azacitidine.
- To assess the impact of treatment on quality of life (QoL) using the European Organisation for Research and Treatment of Cancer (EORTC) QLQ-C30 and EQ-5D-5L.
- To evaluate the PK of AG-120 as administered in combination with azacitidine.
- To evaluate the PK/PD relationship of AG-120 and 2-HG in blood samples in comparison with placebo.

- To compare rates of CR with IDH1 mutation clearance (MC) between AG-120 + azacitidine and placebo + azacitidine.

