6.2.2. Secondary Endpoints

The key secondary endpoints are:

- CR rate (CR defined as bone marrow blasts <5% and no Auer rods, absence of extramedullary disease, ANC $\geq 1.0 \times 10^9/L$ [1000/ μL], platelet count $\geq 100 \times 10^9/L$ [100,000/ μL], and independence of RBC transfusions).
- OS, defined as the time from date of randomization to the date of death due to any cause.
- CR + CRh rate (CRh is defined as a CR with partial recovery of peripheral blood counts where ANC is $>0.5 \times 10^9/L$ [500/ μL], and platelet count is $>50 \times 10^9/L$ [50,000/ μL]; CRh will be derived by the Sponsor).
- ORR, defined as the rate of CR, CRi (including CRp), PR, and MLFS.

Additional secondary endpoints are:

- CR + CRi (including CRp) rate (CRi [including CRp] is defined as all CR criteria except for residual neutropenia where ANC is $<1.0 \times 10^9/L$ [1000/ μL] or thrombocytopenia where platelet count is $<100 \times 10^9/L$ [100,000/ μL]; without platelet transfusion for at least 1 week prior to disease assessment).
- DOCR, among subjects who achieved CR; DOCRh, among subjects who achieved CR or CRh; DOR, among subjects who achieved CR, CRi (including CRp), PR, and/or MLFS; and DOCRi, among subjects who achieved CR or CRi (including CRp).

- TTCR, among subjects who achieved CR; TTCRh, among subjects who achieved CR or CRh; TTR, among subjects who achieved CR, CRi (including CRp), PR, and/or MLFS; and TTCRi, among subjects who achieved CR or CRi (including CRp).
- Vital signs, and results of ECOG PS, ECG, and echocardiogram (ECHO) or multi-gated acquisition (MUGA) for left ventricular ejection fraction (LVEF) as clinically indicated (method per institutional standard of care, with the same method used for an individual throughout the study; sites in Germany may only use ECHO).
- Clinical laboratory assessments (hematology, chemistry, and coagulation).
- AEs, AEs of special interest (AESIs), SAEs, and AEs leading to discontinuation or death.
- Concomitant medication use.
- Transfusion requirements (platelet and RBC; number of units transfused), rates of infection, days spent hospitalized, and other efficacy and safety measures that are potentially indicative of clinical benefit.
- Changes from baseline in QoL assessments (EORTC QLC-C30 and EQ-5D-5L).
- Rates of CR with IDH1 MC.
- AG-120/placebo and azacitidine drug exposure, including dose modifications and dose intensities.
- AG-120 and 2-HG concentrations in circulating plasma.

[REDACTED]

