- 14 Evaluation of disease status, including evaluation of bone marrow and/or peripheral blood, to be conducted: at Screening (or as part of Pre-screening as long as it is within 28 days prior to randomization); Day 1 (\pm 7 days) of Weeks 9, 17, 25, 33, 41, 53, and every 24 weeks thereafter; at EOT; during EFS follow-up on the same schedule; as clinically indicated; and/or any time that disease progression is suspected. Upon Sponsor unblinding, evaluation of disease status will no longer be collected. Subjects are expected to remain on treatment with AG-120/placebo as long as there are no unacceptable toxicities and the subject has a response of at least stable disease. Also includes assessment of transfusions (RBC and platelet), infections, length of any hospital stays, and other efficacy and safety measures that are potentially indicative of clinical benefit. De-identified copies of evaluation reports (bone marrow and/or peripheral blood assessment of disease status) should be submitted. Blood draws for regular hematology assessments (footnote 17) should be reviewed for the need to evaluate disease status at an unscheduled time point.
- 15 Clinically directed examinations, including a skin examination.
- 16 For female subjects with reproductive potential: A serum β -hCG pregnancy test is required at Screening and must be verified as negative within 72 hours prior to study treatment administration. A urine pregnancy test will be conducted on C1D1 and confirmed negative prior to dosing, and on Day 1 of all subsequent cycles. A urine pregnancy test should be conducted at the end of treatment visit.
- 17 Hematology: hemoglobin, RBC count, WBC count with differential, ANC, platelet count, and peripheral blast count. Hematology blood draws should occur prior to administration of any study drugs on visit date.
Chemistry: sodium, potassium, calcium, magnesium, albumin, glucose, BUN, creatinine, lactate dehydrogenase, ALP, AST, ALT, total bilirubin, phosphate, and bicarbonate. Chemistry blood draws should occur prior to administration of any study drugs on visit date.
Blood for hematology and chemistries is to be obtained: at Screening; on Days 1, 8, 15, and 22 (\pm 3 days) of Cycle 1 (Weeks 1, 2, 3, and 4); on Days 1 and 15 (\pm 3 days) of Cycles 2, 3, and 4 (Weeks 5, 7, 9, 11, 13, and 15); on Day 1 (\pm 3 days) of each treatment cycle thereafter (Weeks 17+); at EOT; and 4 weeks post-treatment.

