10.8.2. Indicators of Clinical Benefit

The clinical activity of the combination of AG-120/placebo and azacitidine will also be assessed using surrogate indicators of clinical benefit, including transfusion frequency (dates of the transfusion and units administered), infection rates, days spent hospitalized, and other efficacy and safety measures that are potentially indicative of clinical benefit. At each study visit, the Investigator will record any changes to these parameters.

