11.1. Definition of Adverse Events

11.1.1. Adverse Event

An AE (also referred to as an adverse experience) is any untoward medical occurrence associated with the use of a drug in humans, whether or not considered drug related. An AE can therefore be any of the following:

- Any unfavorable and unintended sign (eg, an abnormal laboratory finding), symptom, or disease temporally associated with the use of a drug, whether or not considered related to the drug.
- Any new disease or exacerbation of an existing disease (a worsening in the character, frequency, or severity of a known condition).
- Recurrence of an intermittent medical condition (eg, headache) not present at baseline.
- Any deterioration in a laboratory value or other clinical test (eg, ECG, X-ray) that is associated with symptoms or leads to a change in study treatment or concomitant treatment or discontinuation from study treatment.
- Adverse events that are related to a protocol-mandated intervention, including those that occur prior to assignment of study treatment (eg, Screening invasive procedures such as biopsies).

An AE can arise from any use of the drug (eg, off-label use, use in combination with another drug) and from any route of administration, formulation, or dose, including an overdose.

Disease progression or death due to disease progression will not be considered an AE (or an SAE) in this study, but will be collected as an outcome or reason for discontinuation, as appropriate. Adverse events (or SAEs) considered as complications of disease progression should be reported. See Section 11.2.7 for more detailed instructions regarding the reporting of disease progression and deaths due to disease progression.

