11.2.9. Hospitalization or Prolonged Hospitalization

Any AE that results in hospitalization or prolonged hospitalization should be documented and reported as an SAE (per the definition of SAE in Section 11.1.3), except as outlined below.

The following hospitalization scenarios are *not considered* to be SAEs:

- Hospitalization for respite care.
- Standard procedure for protocol therapy administration; however, hospitalization or prolonged hospitalization for a complication of therapy administration will be reported as an SAE.
- Routine treatment or monitoring of the studied indication not associated with any deterioration in condition.
- Administration of blood or platelet transfusion as routine treatment of studied indication; however, hospitalization or prolonged hospitalization for a complication of such transfusion remains a reportable SAE.
- A procedure for protocol/disease-related investigations (eg, surgery, scans, endoscopy, sampling for laboratory tests, bone marrow sampling); however, hospitalization or prolonged hospitalization for a complication of such procedures remains a reportable SAE.

- Hospitalization or prolongation of hospitalization for technical, practical, or social reasons, in absence of an AE.
- A procedure that is planned (ie, planned prior to start of treatment on study); must be documented in the source document and the eCRF; hospitalization or prolonged hospitalization for a complication remains a reportable SAE.
- An elective treatment of or an elective procedure for a pre-existing condition, unrelated to the studied indication, which has not worsened from baseline.

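### The SAP specifies an arm summary only for hospitalizations for adverse events, although the endpoint is days in hospital for any cause

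*SAP*

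**What the plan says.** **Objective and endpoint.** Protocol 6.1.2 sets out to compare "infection rates, days spent hospitalized, and other efficacy and safety measures that are potentially indicative of clinical benefit between AG-120 + azacitidine and placebo + azacitidine". Protocol 6.2.2 lists the same measure as an additional secondary endpoint, and Protocol 10.8.2 treats it as a surrogate indicator of clinical benefit. Protocol 12.5.2.2.4 plans descriptive statistics by arm. None of these limits the stays by cause.

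**Data collection.** Footnote 14 to Table 6 (Protocol 10.1) says of the disease evaluation: "Also includes assessment of transfusions (RBC and platelet), infections, length of any hospital stays".

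**Analysis.** The lead-in to SAP 7.8.8 again promises days in hospital by treatment arm with no restriction. SAP 7.8.8.1.2, headed Hospitalizations for Adverse Event, then gives the only operational rule: "Hospitalizations for AE will be summarized, including number of events, total number of days hospitalized, the rate of events and days hospitalized per person-year". It adds a by-subject listing of hospitalizations, which is not restricted to adverse events.

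**What counts as an adverse event.** Protocol 11.1.1 states: "Disease progression or death due to disease progression will not be considered an AE (or an SAE) in this study". Protocol 11.2.9 lists stays that are not SAEs, among them "Administration of blood or platelet transfusion as routine treatment of studied indication".

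**The concern.** A programmer who builds the table from SAP 7.8.8.1.2 will deliver stays linked to an adverse event, not total time in hospital. That does not answer the stated objective. Part of the hospital burden of the disease would be missing from the arm comparison, while admissions for drug toxicity, such as Grade 2 or higher differentiation syndrome (Protocol 9.9.2), would be kept.

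The protocol itself treats hospital use as reflecting disease benefit. In Protocol 5.3 it cites fewer hospitalizations among subjects without CR in the earlier phase 3 azacitidine trial. An adverse-event count is a different quantity, and the SAP gives no reason for substituting it.

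The rate per person-year has a further gap: SAP 7.8.8.1.2 states neither an observation period nor a denominator.

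**Working it through.** The plan gives no rate, effect size or power for days in hospital, so there is no figure to reproduce. The check is a reconciliation of the text, followed by an illustration on assumed inputs.

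**1. Which stays reach the arm summary in SAP 7.8.8.1.2?**

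| Kind of stay | Status in the protocol | In the arm summary? |
|---|---|---|
| Drug toxicity | AE | Yes |
| Complication of progression | AE or SAE to be reported (11.1.1) | Yes |
| Grade 3 or higher leukocytosis | AE of special interest (11.2.3.2) | Yes |
| Unclear whether due only to the leukemia | Reported as AE or SAE (11.2.7) | Yes |
| Clearly and solely progression of AML | Not an AE (11.1.1, 11.2.7) | No |
| Transfusion stay with a reported AE beneath it | Not an SAE (11.2.9), but a laboratory abnormality that leads to an intervention is an AE (11.2.5) | Can be counted |
| Routine disease care, transfusion, drug administration, respite or social stay with no AE beneath it | Not an SAE (11.2.9), and no AE to link it to | No |

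The fifth and last rows are what is lost. They remain in the listing only.

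**2. Is the narrowing consistent with the rest of SAP 7.8.8?** No. The lead-in is unrestricted. The neighbouring subsection on transfusions (SAP 7.8.8.1.1) counts every transfusion started in the on-treatment period and tabulates the reasons. Only hospitalization is tied to adverse events.

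**3. How much could it matter?** All inputs here are assumed; none comes from the documents. Let A be AE-related days per person-year, equal in both arms, at 20 or 40. Let c and t be days solely due to progression in the control and AG-120 arms, with (c, t) = (2, 1), (5, 2) or (10, 4).

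- AE-only ratio, AG-120 to control: A / A = 1.00 in every case.
- All-cause ratio: (A + t) / (A + c). The extremes are (40 + 1) / (40 + 2) = 0.98 and (20 + 4) / (20 + 10) = 0.80.
- Share of control-arm days omitted: c / (A + c). The extremes are 2 / 42 = 5% and 10 / 30 = 33%.

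The direction comes entirely from assuming c > t. With the same non-AE days exchanged between arms, as could happen if the omitted days were mostly drug-administration stays and one arm stayed on treatment longer, the all-cause ratio runs from 42 / 41 = 1.02 to 30 / 24 = 1.25. The illustration shows that the two definitions can differ. It does not show which arm the AE-only version would favour.

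**The case against.** Several objections have force.

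- **The SAP does not expressly exclude other stays.** The lead-in to 7.8.8 still promises an unrestricted summary, and the listing covers all hospitalizations. This stands: the fault is a conflict inside the SAP. But only 7.8.8.1.2 says what to compute, so the conflict needs resolving.
- **A reader might infer that admissions for uncontrolled leukemia are left out altogether.** The documents do not support that. Complications of progression are to be reported, and uncertain cases default to AE or SAE. Protocol 11.2 names neutropenia, thrombocytopenia, anemia and infections as anticipated SAEs and waives only their individual expedited reporting. The loss is confined to stays attributed clearly and solely to progression and to care or social stays without an AE.
- **A reader might infer that every stay listed in Protocol 11.2.9 adds zero days.** That does not follow either. The section defines what is not an SAE, whereas the SAP counts stays for an AE.
- **A reader might infer bias against the arm that controls the leukemia better,** because the design assumes that 1 - 0.20 = 80% of control and 1 - 0.40 = 60% of AG-120 subjects have no CR by Week 24 (Protocol 12.12). Lack of CR is not progression: it includes CRi, PR, MLFS and stable disease, and such subjects may continue treatment if they show benefit. Respite, social and administration stays are not failures of disease control.
- **The SAP may modify the protocol's plans (SAP 2).** True, but a deliberate change would not leave the unrestricted promise standing a few lines above it.
- **Widening the table may not recover stays after relapse or treatment failure.** Subjects with those events do not enter EFS follow-up (Protocol 8.5.2), and Table 6 shows no disease evaluation in survival follow-up. This stands as a limit on any remedy.

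**Conclusion.** The point holds in a limited form. The specified arm summary is narrower than the protocol's objective, endpoint and planned analysis, narrower than the data sites are asked to collect, and narrower than the SAP's own lead-in. Followed literally, it would not deliver days in hospital as the protocol defines the measure.

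The size is unknown. Under the assumed inputs, between 5% and 33% of control-arm days would be omitted, but the documents give no share of non-AE stays. Neither the magnitude nor the direction of any bias can be stated.

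The consequence is contained. This is an additional secondary, descriptive measure outside the fixed-sequence procedure, with no alpha control (Protocol 12.5). EFS, the key secondary endpoints, the sample size and the decision rule are unaffected. The correction is still worth making, because it is cheap and restores a stated objective.

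**What to change.** In SAP 7.8.8.1.2:

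1. Drop the restriction from the heading and the rule. Summarize all-cause hospitalizations by arm: number, total days, and events and days per person-year.
2. Show AE-related and non-AE stays as sub-rows, so that the table now specified is kept inside the wider one.
3. State the observation period and the matching denominator. The on-treatment period of SAP 6.3.5, already used for transfusions, is the natural choice, with person-years summed over the same period.
4. Note that stays after relapse or treatment failure may not be captured.

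The cost is SAP wording and one wider descriptive table. The protocol already requires the length of any stay to be assessed. The eCRF is not among the documents, so confirm that the hospitalization record holds dates and a reason for each stay.

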7.9. Biomarker Analyses

7.9.1. Methods

Genomic DNA from baseline and on-treatment bone marrow mononuclear cells (BMMCs) and/or peripheral blood mononuclear cells (PBMCs) will be used for molecular studies. mIDH1 VAF will be quantified through BEAMing digital PCR (dPCR) technology (OncoBEAM™; Sysmex Inostics, Baltimore, MD, USA) for assessment of R132 (C/G/L/S/H) alleles. A valid mIDH1 VAF result is defined as a VAF value other than “not evaluable”. IDH1 MC is defined as mIDH1 VAF reduction to below the lower limit of detection (0.02%-0.04%) for at least one on-treatment time point.

7.9.2. Statistical Analyses

Complete remission with IDH1 MC is defined as a response of CR where there is no evidence of the IDH1 mutation by molecular techniques to below the lower limit of detection (0.02%-0.04%) for ≥ 1 on-treatment time point. A CMH test stratified by the randomization stratification factors will be used to compare the rate of CR with IDH1 MC between the 2 treatment arms and the nominal 1-sided p-value will be presented. The odds ratio and its associated 95% CI will be presented.

IDH1 MC by sample type (BMMCs and PBMCs) and treatment arm will be summarized in a table by best objective response. The difference in percent of subjects who achieved IDH1 MC in each sample type and treatment arm will be compared between subjects achieving CR to subjects not achieving CR as best objective response using a Fisher’s exact test.

7.10. Interim Analyses

There are no interim analyses for efficacy planned for this study.

Safety data will be reviewed regularly by an I-DMC to ensure the safety of the combination therapy. These reviews will occur after the first 6, 12, 24, and 36 subjects have completed 1 cycle of therapy or discontinued, whichever should occur first. Thereafter, safety reviews

will be conducted approximately every 6 months until the study is unblinded for the analysis of the primary endpoint.

